7. STUDY PROCEDURES

A summary of all study required procedures and assessments can be found in Appendix 1.

7.2 Laser Treatment 1 to 6 – Visit Window and Pre-Treatment Procedures

Cutera, Inc.

Protocol # C-17-ML02

“Open-label, Prospective, Multicenter Study to Evaluate the Cutera enlighten™ Laser and a Micro-Lens Array Handpiece Attachment for the Treatment of Moderate and Severe Acne Scars”

Confidential and Proprietary

Page 17 of 37

Version 1.0; 17JUL2017

[REDACTED]

7.4 Phone and Follow-Up Visits

There are [REDACTED] follow-up visits at [REDACTED] and 12 weeks [REDACTED] () following the final laser treatment.

The following procedures will be performed during the phone and follow-up visits:

1. Assessment of Concomitant Medications: Assess and record any additions, changes and/or deletions in prescription and nonprescription concomitant medications since the previous study visit.
2. Assess for any ongoing, previously reported, and/or new adverse events and expected adverse device effects.

During the follow-up visits:

1. Cleanse subject's treated area with a mild cleanser to remove any cosmetics, lotions, or perfumes.
2. Photographs of the treated area(s) will be taken at the same pre-defined angles (Section 5.5).
3. Investigator will assesses the efficacy of the Cutera enlighten laser with the Micro-Lens Array handpiece attachment treatment using the ASAS, [REDACTED]

8. ADVERSE EVENTS and ADVERSE DEVICE EFFECTS

8.1 Definitions

[REDACTED]

[REDACTED]

[REDACTED]

[REDACTED]

Cutera, Inc.

Protocol # C-17-ML02

"Open-label, Prospective, Multicenter Study to Evaluate the Cutera enlighten™ Laser and a Micro-Lens Array Handpiece Attachment for the Treatment of Moderate and Severe Acne Scars"

[REDACTED]

[REDACTED]

[REDACTED]

[REDACTED]

[REDACTED]

Cutera, Inc.

Protocol # C-17-ML02

“Open-label, Prospective, Multicenter Study to Evaluate the Cutera enlighten™ Laser and a Micro-Lens Array Handpiece Attachment for the Treatment of Moderate and Severe Acne Scars”

8.2 Recording AEs, ADEs and SADEs

All AEs/SAEs or ADEs/SADEs will be: (1) evaluated and must be recorded in the subject's medical chart and in the study case report forms (CRFs); (2) monitored and tracked from the time of the first treatment with the Cutera Enlighten laser system.

At each contact with the subject, the investigator must seek information on AEs/ADEs/SADEs by specific questioning and, as appropriate, by examination. AEs/ADEs/SADEs may be observed by the investigator and/or clinical research staff, elicited from the subject and/or family member or volunteered by the subject. All observed and volunteered adverse signs and symptoms, anticipated or unanticipated, regardless of severity or frequency, will be recorded in the case histories (medical chart and CRFs). Included in the description should be the nature of the sign or symptom, the date of onset, date of resolution (duration), the severity, anticipated or unanticipated, the relationship to study treatment or other therapy, the action taken (if any), and the outcome.

All SAEs/SADEs, anticipated or unanticipated, must be reported to Cutera immediately but not later than 5 working days. The SADE must be recorded in: (1) the AE CRF and (2) a written report must be submitted to Cutera within five (5) working days after the investigator first learns of the event and is to include a full description of the event and sequelae, in the format detailed by the Cutera Serious Adverse Event Form.

8.3 Follow-up of subjects after AEs/ADEs and SAEs/SADEs:

All reported AEs/ADEs/SAEs/SADEs should be followed until resolution or until the subject's participation in the study ends. Resolutions of AEs/ADEs/SAEs/SADEs are to be documented on the appropriate CRFs. All ADEs that result in permanent discontinuation from this clinical trial, whether serious or not, should also be reported on the subject Non-Completion of Study Form.

9. POTENTIAL RISKS / BENIFITS

A 10x4 grid of black and white blocks. The first column contains a large black block with white borders on the left and bottom, and white blocks above and to its right. The other three columns are entirely black.

For more information, contact the Office of the Vice President for Research and the Office of the Vice President for Student Affairs.

Digitized by [contact]

9.2 Potential Benefits

The subjects may or may not benefit from the treatment with the study device. Potential benefit of laser treatment for acne scars is improved appearance of treated area. There is no guarantee of success.

10. RISK MANAGEMENT

The investigator participating in this study was chosen based on extensive and safe experience with the use of lasers in dermatology applications. This is the most critical element in managing subject risk. In addition, study investigators will be trained on the use of the Cutera Enlighten laser system by a representative of Cutera.

11. DATA ANALYSIS PLAN

11.1 Sample Size

The primary objective is to show that the response rate (as defined below) is significantly greater than 50%. Under the assumption that the true population response rate is 75%, 40 subjects will provide 80% power to reject the primary hypothesis. To allow for up to a 10% dropout rate, 45 subjects will be treated.

11.2 Demographics and Subject Characteristics at Baseline

Subject demographics, medical history, concomitant medications will be tabulated and summarized descriptively.

11.3 Statistical Analysis Methods

This is a study to evaluate safety and efficacy of the Cutera enlighten laser with the Micro-Lens Array handpiece attachment. Outcome measures will be assessed around multiple endpoints. These measures will be: degree of improvement as assessed by the Investigator, blinded evaluators, [REDACTED] and safety. Additional assessments may also be performed but are not considered part of the analysis (i.e. Subject post-treatment questionnaire).

11.3.1 Analysis Sets

The efficacy analysis set will include all subjects who received one facial laser treatment session and complete at least one follow-up visit. The safety analysis set will include all subjects enrolled in the study who had at least one laser treatment session.

Missing data will not be imputed for efficacy or safety endpoints.

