5.1.3 Safety Endpoints

- Safety of the Cutera enlighten laser with Micro-Lens Array handpiece attachment as assessed by the frequency and severity of device related adverse events.

[REDACTED]

[REDACTED]

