11.3.4 Safety Analyses

Safety variables will be analyzed descriptively. The safety variables for this study are:

- Incidence and severity of adverse effects during study duration (to be displayed descriptively as counts and frequency distributions)

Enrolled subjects who received at least one treatment will be included in the safety analyses. Device-related and procedure-related adverse effects (AEs) and subjects who prematurely terminate from the study due to an adverse device effect, including the treatment-related pain ratings, as reported on case report forms will be tabulated and analyzed. For a given AE term, counting will be done by subject, not by event, i.e. for a subject reporting the same AE more than once, the event will be counted only once, at the most severe and most-related occurrence. The number and percentage of subjects experiencing each AE Term will be descriptively summarized. Statistical hypothesis testing will not be performed for safety data.

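### The no-imputation rule covers safety, so an adverse event with a blank relationship is left out of the device-related count, and that rate can only fall or stay the same

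*Combined protocol and SAP*

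**What the plan says.** Four parts of the combined protocol and SAP bear on this.

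- **Section 11.3.1 (Analysis Sets)** gives the missing-data rule: "Missing data will not be imputed for efficacy or safety endpoints". It names safety expressly. The safety set is every enrolled subject with at least one laser session.
- **Section 5.1.3 (Safety Endpoints)**, like the Protocol Summary, has safety "assessed by the frequency and severity of device related adverse events".
- **Section 11.3.4 (Safety Analyses)** lists the safety variable more broadly: "Incidence and severity of adverse effects during study duration (to be displayed descriptively as counts and frequency distributions". It tabulates device-related and procedure-related effects. It counts by subject within each term, so that for repeat reports "the event will be counted only once, at the most severe and most-related occurrence". It adds: "The number and percentage of subjects experiencing each AE Term will be descriptively summarized". It also puts treatment-related pain ratings among the safety data and rules out hypothesis testing.
- **Section 8.2 (Recording AEs, ADEs and SADEs)** asks that each event's description include "the severity, anticipated or unanticipated, the relationship to study treatment or other therapy, the action taken (if any), and the outcome".

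No visible section says how to classify or display an event whose relationship or severity was not recorded. The scale in section 5.4.1 has three grades (mild, moderate, severe) and no unknown category. The definitions in section 8.1 are redacted.

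**The concern.** A no-imputation rule is usually proposed as the cautious choice. For a safety endpoint that admits events only through a classification field, it is not neutral. Unless a blank relationship is assigned, the event cannot be shown to be device-related and does not enter that count. The resulting error has one direction, towards a lower device-related rate. The study has a single arm, so there is no comparator in which the same loss would occur.

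Blanks are possible, though they should be few. Section 8.2 words the content of the event description as something that should be included. Section 6.3 says only that the investigator will attempt a final adverse device effect evaluation when a subject withdraws, and section 11.1 allows for up to 10% dropout.

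At stake is the device-related rate in a pivotal study of about 45 people, where one subject can separate none observed from one observed. Without a written rule, the classification would be chosen after the data are seen.

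**Working it through.** **Denominator.** Section 11.1 gives 40 subjects and up to 10% dropout: 40 / (1 − 0.10) = 44.4, rounded up to 45. The plan's figure of 45 treated reproduces. All treated subjects are in the safety set, so n = 45.

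The documents give no figure for missing relationship or severity. All event counts below are assumptions chosen to show size and direction.

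**Blank relationship.** Let *r* be the number of subjects with a given term recorded as device-related, and *b* the number whose only possibly related occurrence of that term has a blank relationship. Leaving blanks out gives *r*/45. Counting them as related gives (*r* + *b*)/45. The difference, *b*/45, is never negative and is 1/45 = 2.2 points per subject. With *r* = 5:

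| *b* | Blanks left out | Blanks counted as related |
|---|---|---|
| 1 | 5/45 = 11.1% | 6/45 = 13.3% |
| 2 | 5/45 = 11.1% | 7/45 = 15.6% |
| 3 | 5/45 = 11.1% | 8/45 = 17.8% |

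If the subject has another occurrence of the same term recorded as related, the most-related counting rule already counts that subject, and the shift is zero. For a rate of any device-related event, the shift is zero if the subject has a related event of any term.

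**Extreme case, *r* = 0.** Exact (Clopper-Pearson) 95% limits for *x* of 45 are the 2.5% quantile of Beta(*x*, 46 − *x*) and the 97.5% quantile of Beta(*x* + 1, 45 − *x*). For *x* = 0 the lower limit is 0 and the upper limit is 1 − 0.025^(1/45).

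| *x* | Rate | Upper limit |
|---|---|---|
| 0 | 0% | 7.9% |
| 1 | 2.2% (lower limit 0.06%) | 11.8% |
| 2 | 4.4% | 15.1% |

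The plan specifies no safety interval. These limits only show how much a single subject can matter for a rare event.

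**Blank severity.** Assume 12 mild, 6 moderate, 2 severe and 1 blank, each in a different subject.

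| Measure for severe | Blank left out | Blank truly severe | Blank truly mild |
|---|---|---|---|
| Share of safety set | 2/45 = 4.4% | 3/45 = 6.7% | 2/45 = 4.4% |
| Share of graded events | 2/20 = 10.0% | 3/21 = 14.3% | 2/21 = 9.5% |

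On the safety-set denominator, leaving the blank out lowers a grade's figure or leaves it unchanged. On the graded-events denominator, it understates the severe share if the blank was severe (10.0% against 14.3%) and overstates it slightly if the blank was mild (10.0% against 9.5%).

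**Where the event still appears.** The per-term number and percentage in section 11.3.4 need neither field, so an event with a blank relationship or severity is still counted there.

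**The case against.** The strongest objection is that section 11.3.1 says only that values are not imputed. It does not say that an event is excluded or treated as unrelated, and a separate row for a missing classification would comply with it. This stands as a caution: omission follows from a literal reading and is not stated. It does not remove the point, because an event shown in a missing row is still outside the device-related count, and the plan specifies no such row.

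Four further points limit the concern:

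- The event is not lost. A reader might infer that a rare harm could disappear from the report. The per-term summary in section 11.3.4 does not support that.
- Section 8.2 requires all events to be evaluated and recorded, with specific questioning at each contact, so blanks should be few. Nothing in the documents shows that they would cluster in subjects who leave early. Classification rules may exist in the redacted section 8.1.
- Counting at the most severe and most-related occurrence is already conservative where another occurrence supplies the field.
- Safety is descriptive, so no test result or decision rule changes.

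It is also fair to object to removing safety from the no-imputation sentence altogether: pain ratings would then have no missing-data rule. Coding every blank severity as severe in the main table would assert a grade without evidence. The fix allows for both.

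**Conclusion.** The point holds in a limited form. Under a literal reading of section 11.3.1, an adverse event with no recorded relationship stays out of the device-related count, and the error runs only downward. At n = 45 it is 2.2 points per affected subject, provided that the subject has no other related occurrence of the term. The effect is confined to the device-related tables.

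A reader might infer that blanks in both fields always favour the device. That does not hold for severity: counts and safety-set percentages can only fall or stay the same, but shares of graded events can move either way.

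The conclusion assumes that no classification rule exists in the redacted text and that some blanks occur. The number of blanks is unknown and is probably small. This is an inexpensive improvement to the plan and does not bear on the validity of the study.

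**What to change.** Keep the sentence in section 11.3.1, so that it continues to cover efficacy and the pain ratings. Add to section 11.3.4, as a stated exception:

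1. An adverse event with missing relationship is counted as device-related.
2. An adverse event with missing severity is shown in its own row of the severity table. A worst-case sensitivity table counts it as severe.
3. A footnote to each table gives the number of events affected.

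This takes a few sentences of text and one additional table, and should be written before the data are seen. The downside is that the reported device-related rate may be slightly less favourable, because some events counted as related may not have been. The footnote lets the reader judge how much.

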11.3.2 Primary Efficacy Analysis

The primary endpoint is a responder, where a clinical response is defined as at least two of the three blinded reviewers selecting the correct order of treatment with at least a one-point improvement in the ASAS from baseline to 12 weeks. The primary hypothesis is as follows:

$H_0: \Pi = 0.5$

vs.

$H_A: \Pi \neq 0.5$,

where Π is the population response rate. The primary analysis will place an exact two-sided 95% confidence interval around the observed response rate and compare the lower bound to 50%. If the lower bound exceeds 50% the primary hypothesis will be rejected in favor of the response rate being greater than 50%.

11.3.3 Analysis of Secondary Endpoints

[REDACTED]

[REDACTED]

[REDACTED]

11.3.4 Safety Analyses

Safety variables will be analyzed descriptively. The safety variables for this study are:

- Incidence and severity of adverse effects during study duration (to be displayed descriptively as counts and frequency distributions)

Enrolled subjects who received at least one treatment will be included in the safety analyses. Device-related and procedure-related adverse effects (AEs) and subjects who prematurely terminate from the study due to an adverse device effect, including the treatment-related pain ratings, as reported on case report forms will be tabulated and analyzed. For a given AE term, counting will be done by subject, not by event, i.e. for a subject reporting the same AE more than once, the event will be counted only once, at the most severe and most-related occurrence. The number and percentage of subjects experiencing each AE Term will be descriptively summarized. Statistical hypothesis testing will not be performed for safety data.

12. SUBJECT PAYMENT

A large black rectangular box redacting a section of the document.

13. STUDY MANAGEMENT AND ADMINISTRATIVE PROCEDURES

A large black rectangular box redacting a section of the document.
A large black rectangular box redacting a section of the document.

13.2 Informed Consent

A large black rectangular box redacting a section of the document.
A large black rectangular box redacting a section of the document.

[REDACTED]

[REDACTED]

[REDACTED]

[REDACTED]

13.3 Protocol Compliance

The principal investigator must comply with all terms of the protocol.

13.4 Protocol Amendments

Neither the principal investigator nor the sponsor will modify or alter this protocol without first obtaining the concurrence of the other party (with the exception of amendments which involves mitigating a medical emergency or immediate health risk to the subject). The party initiating an amendment must confirm it clearly in writing and it must be signed and dated by the sponsor and the principal investigator. IRB approval must be obtained before implementation of an amendment.

13.5 Protocol Deviations

All protocol deviations must be clearly described on the case report form (i.e., Cutera Protocol Deviation Form). Deviations from the protocol may include but are not limited to subject's failure to attend scheduled visit during a visit window, use of out of range treatment parameters and incomplete or incorrect study procedures. Any medical emergency or immediate health risk to the subject which results in a protocol deviation and must be reported to the sponsor within 5 working days

Significant protocol deviations must be reported to IRB according to their policies.

13.6 Study Personnel

The investigator must supply the sponsor with a list of the names and curricula vitae that describe the professional backgrounds of the clinically responsible study investigators (principal, sub-investigators), research nurses, and other possible participants (e.g. medical doctor, nurse, etc.).

13.7 Disclosure of Financial Interest

[figure not shown]
[figure not shown]
Each investigator [principal and sub-investigator(s)] is required to disclose sufficient accurate financial information to the sponsor, to allow sponsor to submit complete and accurate certification or disclosure statements.

13.8 Data Collection, Record Keeping and Storage

14. SUBJECT CONFIDENTIALITY

This study preserves the confidentiality of all subjects under the Health Insurance Portability and Accountability Act of 1996 (HIPAA) Privacy Rule. The following safeguards will be in place to protect the privacy of the individuals who are the subjects of the health information to be used in the research and the confidentiality of that information:

15. PUBLICATION POLICY

The investigator shall have the right to publish the results of the study. Unless mutually agreed upon in writing, prior to submission for publication of any manuscript, poster, presentation, abstract or other written or oral material describing the results of the study, the investigator shall allow sponsor to review manuscript, poster presentation, abstract or other written or oral material which describes the results of the study for the purpose only of determining if any patentable information is disclosed. At the sponsor's request, the investigator shall withhold any publication or presentation to permit sponsor to seek patent protection and to remove any confidential information from all publications.

The International Committee of Medical Journal Editors (ICMJE) member journals have adopted a trials registration policy as a condition for publication. This policy requires that all clinical trials be registered in a public trials registry such as ClinicalTrials.gov, which is sponsored by the National Library of Medicine. It is the responsibility of the sponsor to register this trial in ClinicalTrials.gov. Any clinical trial starting enrollment after September 27, 2007 must be registered either on or before the onset of patient enrollment.

REFERENCES

Cutera, Inc.

Protocol # C-17-ML02

"Open-label, Prospective, Multicenter Study to Evaluate the Cutera enlighten™ Laser and a Micro-Lens Array Handpiece Attachment for the Treatment of Moderate and Severe Acne Scars"

Cutera, Inc.

Protocol # C-17-ML02

“Open-label, Prospective, Multicenter Study to Evaluate the Cutera enlighten™ Laser and a Micro-Lens Array Handpiece Attachment for the Treatment of Moderate and Severe Acne Scars”

Cutera, Inc.

Protocol # C-17-ML02

“Open-label, Prospective, Multicenter Study to Evaluate the Cutera enlighten™ Laser and a Micro-Lens Array Handpiece Attachment for the Treatment of Moderate and Severe Acne Scars”

Cutera, Inc.

Protocol # C-17-ML02

"Open-label, Prospective, Multicenter Study to Evaluate the Cutera enlighten™ Laser and a Micro-Lens Array Handpiece Attachment for the Treatment of Moderate and Severe Acne Scars"

Cutera, Inc.

Protocol # C-17-ML02

“Open-label, Prospective, Multicenter Study to Evaluate the Cutera enlighten™ Laser and a Micro-Lens Array Handpiece Attachment for the Treatment of Moderate and Severe Acne Scars”

Cutera, Inc.

[figure not shown]
Protocol # C-17-ML02

“Open-label, Prospective, Multicenter Study to Evaluate the Cutera enlighten™ Laser and a Micro-Lens Array Handpiece Attachment for the Treatment of Moderate and Severe Acne Scars”

Cutera, Inc.

Protocol # C-17-ML02

"Open-label, Prospective, Multicenter Study to Evaluate the Cutera enlighten™ Laser and a Micro-Lens Array Handpiece Attachment for the

Cutera, Inc.

Protocol # C-17-ML02

"Open-label, Prospective, Multicenter Study to Evaluate the Cutera enlighten™ Laser and a Micro-Lens Array Handpiece Attachment for the Treatment of Moderate and Severe Acne Scars"

Cutera, Inc.

Protocol # C-17-ML02

"Open-label, Prospective, Multicenter Study to Evaluate the Cutera enlighten™ Laser and a Micro-Lens Array Handpiece Attachment for the

[REDACTED]

[REDACTED]

[REDACTED]

| [REDACTED]

| [REDACTED]

[REDACTED]

| [REDACTED]

| [REDACTED]

| [REDACTED]

| [REDACTED]

| [REDACTED]

| [REDACTED]

|| [REDACTED]

| [REDACTED]

[REDACTED]

[REDACTED]

[REDACTED]
